4.5.2 Adverse Events

All verbatim AEs terms will be coded using the latest version of Medical Dictionary for Regulatory Activities (MedDRA).

For safety analyses, unless otherwise specified, only treatment-emergent AEs will be included in the analyses. Treatment-emergent AEs will be defined as any new AEs reported or any worsening of an existing condition on or after the infusion of Obinutuzumab or placebo post randomization (excluding AEs reported in the eCRF as occurred prior to the first study drug administration) through the completion of the study

or until a patient discontinues study prematurely. Adverse events with missing onset date will be considered to be treatment emergent. Adverse events with partially missing onset date will also be included as treatment emergent when the month (if it was recorded) and the year occur on or later than the month and year of the study treatment start date.

AEs will be summarized by system organ class (SOC) and preferred term (PT), and will be presented in order of descending frequency summed across the treatment groups within each SOC and PT. For each treatment group, the incidence count for each AE PT will be defined as the number of patients reporting at least one treatment-emergent occurrence of the event (multiple occurrences of the same AE in 1 patient will be counted only once). The proportion of patients with an AE will be calculated as the incidence count divided by the total number of patients in the population. Each table will also present the total number of AEs reported where multiple occurrences of the same AE in an individual are counted separately.

The following will be summarized, and/or listings produced where required:

- All AEs
- SAEs
- AEs by relationship to obinutuzumab/placebo
- AEs by relationship to MMF
- AEs leading to blinded obinutuzumab discontinuation
- AEs leading to MMF discontinuation
- AEs by NCI CTCAE grade
- Infections
- Serious Infections
- Adverse events of special interest (AESIs) as defined in Section 5.2.3 of the protocol
 - Infusion Related Reactions (IRRs)
 - Grade 3–5 infections
 - Any hepatitis B reactivation or Progressive Multifocal Leukoencephalopathy (PML)
 - Drug-related neutropenia
 - Drug-related thrombocytopenia
 - Gastrointestinal perforations
 - Worsening of pre-existing cardiac conditions
 - Cases of potential drug-induced liver injury that include an elevated ALT or AST in combination with either an elevated bilirubin or clinical jaundice, as defined by Hy's Law

- Suspected transmission of an infectious agent by the study drug
- AEs leading to study discontinuation
- AEs leading to death
- AEs leading to blinded obinutuzumab dose interruption
- AEs leading to MMF dose modification or interruption
- COVID-19 AEs

For key safety events, the AE rates per 100 patient-years exposure will be calculated with 95% CIs by treatment groups, using all occurrences of adverse events. The rate of AEs per 100 patient years is calculated as:

(Total Number of AEs/Total Number of Patient Years at Risk)×100

All summaries and listings of AEs will be listed in the List of Planned Outputs (LoPO).

4.5.3 Laboratory Data

4.5.3.1 Safety Laboratory Parameters

Summary statistics for the absolute and change from baseline values will be produced by visit and treatment group for laboratory parameters.

Laboratory abnormalities will be summarized by visit and treatment group. Summaries by NCI CTCAE grade will also be produced for certain lab assessments, including shift tables from baseline to highest grade post-baseline.

All summaries and listings of laboratory data will be based on the safety-evaluable population and specified in the LoPO.

4.5.3.2 Immunoglobulins

The absolute values and change from baseline will be summarized by treatment group and visit for total Immunoglobulin (Ig), IgA, IgG, and IgM.

The proportion of patients with a value of IgA, IgG, and IgM which is less than the lower limit of normal per visit will be produced.

4.5.3.3 Lymphocyte Populations

The absolute values and change from baseline will be summarized by treatment group and visit for CD3⁺ T-cells, CD3⁺CD8⁺ cytotoxic T-cells, CD3⁺CD4⁺ helper T-cells, and CD16⁺CD56⁺ natural killer cells.

4.5.4 Vital Signs

Vital signs are measured at each scheduled visit in accordance with the schedule of assessments (see protocol): baseline, Week 2, Week 4, Week 24, Week 26, Week 50, Week 52, and Week 76. At infusion visits, vital signs should be taken pre-infusion, then every 15 minutes for 1 hour, then every 30 minutes until the end of the infusion, and

within 30 minutes post-infusion. Additional readings may be obtained at the discretion of the investigator.

Changes in vital signs from baseline will be summarized by visit.

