5.1.1 Risks Associated with Obinutuzumab

5.1.1.1 Infusion-Related Reactions

The most frequently observed adverse drug reactions in patients who received obinutuzumab during clinical studies in CLL and NHL were IRRs, which occurred predominantly during infusion of the first 1000 mg. In patients who received the combined measures for prevention of IRRs (adequate glucocorticoid, oral analgesic/antihistamine, omission of antihypertensive medication in the morning of the first infusion, and, for CLL patients only, the Cycle 1 Day 1 dose administered over 2 days), a decreased incidence of all grade IRRs was observed. The rates of Grades 3–4 IRRs (which were based on a relatively small number of patients) were similar before and after mitigation measures were implemented. The incidence and severity of infusion-related symptoms decreased substantially after the first 1000 mg was infused, with most patients having no IRRs during subsequent administrations of obinutuzumab.

In the majority of patients, IRRs were mild to moderate and could be managed by the slowing or temporary halting of the first infusion, but severe and life-threatening IRRs requiring symptomatic treatment have also been reported. IRRs may be clinically indistinguishable from IgE-mediated allergic reactions (e.g., anaphylaxis).

In studies where patients received either obinutuzumab or rituximab (another anti-CD20 monoclonal antibody), obinutuzumab patients appeared to have more IRRs compared to those receiving rituximab in patients being treated for hematologic malignancies.

In the NOBILITY study, at the Week 76 data cut, obinutuzumab was associated with increased non-serious infusion-related reactions (16% obinutuzumab vs. 10% placebo). All IRRs in obinutuzumab arm were non-serious. Of the 10 patients, the IRRs occurred at the first infusion in 8 patients; all IRRs resolved and none led to obinutuzumab discontinuation.

Details regarding management of IRRs can be found in Section 5.1.3.

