- d Blood pressure and pulse rate (while patient is seated for 5 minutes), respiratory rate, and body temperature. Vital signs should be taken pre-infusion, then in seated or semi-supine position, every 15 minutes for 1 hour, then every 30 minutes until the end of the infusion, and within 30 minutes post-infusion. Additional readings may be obtained at the discretion of the investigator.
- e While the patient weight should be measured in order for the central laboratory to be able to calculate creatinine clearance, for these specific visits (Weeks 24 and 50), the weight does not need to be captured in the eCRF.
- f A complete physical examination, performed at screening, should include an evaluation of the head, eyes, ears, nose, and throat, and the cardiovascular, dermatologic, musculoskeletal, respiratory, gastrointestinal, genitourinary, and neurologic systems. Any abnormality identified at baseline should be recorded on the General Medical History and Baseline Conditions eCRF.
- ⁹ Limited, symptom-directed physical examinations should be performed at specified post baseline visits and as clinically indicated. Changes from baseline abnormalities should be recorded in patient notes. New or worsened clinically significant abnormalities should be recorded as adverse events on the Adverse Event eCRF.

Table 1 Schedule of Activities through Week 76 (cont.)

- ^h If a chest X-ray or CT scan has been obtained within the past 3 months and no clinically significant abnormality was observed and no new pulmonary signs or symptoms are exhibited, no chest X-ray is required.
- ¹ Hematology: CBC, RBC count, WBC count and differential, hemoglobin, hematocrit, mean corpuscular volume, mean corpuscular hemoglobin, and quantitative platelet count.
- Jerum chemistries include AST/SGOT, ALT/SGPT, alkaline phosphatase, total protein, albumin, cholesterol, total bilirubin, BUN, uric acid, creatinine, random glucose, lactate dehydrogenase, potassium, sodium, chloride, calcium, and phosphorus, CPK, cystatin C, and triglycerides. At screening, amylase and lipase will be also included.
- For women of childbearing potential, including those who have had a tubal ligation, a negative urine pregnancy test is required prior to all study drug infusions. If a urine test is positive, results will be confirmed with a serum pregnancy test prior to study drug administration. Study drug infusion must not be administered unless the serum pregnancy test result is negative.

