3.1.4 Pharmacokinetic-Evaluable Population

The pharmacokinetic-evaluable population (PK population) will include all patients who have been randomized to and received any dose of obinutuzumab given as study medication, have at least one post-dose PK sample that is evaluable.

4. STATISTICAL ANALYSES

The primary analysis will be performed when all patients have completed the Week 76 visit or have withdrawn early from the study prior to Week 76, all data collected through

Week 76 are in the database, and the data have been cleaned and verified. At the time of the primary analysis, the study will be ongoing. General Consideration

Analyses of the primary and secondary efficacy endpoints will be stratified by race and region unless otherwise noted. The stratification factors as recorded in IxRS will be used.

All the endpoints will be analyzed and all outputs will presented by combined obinutuzumab and placebo treatment group unless otherwise specified. The treatment group in the document refers to combined obinutuzumab versus placebo group.

Visit windows will be continuous from the midpoint between two consecutive study visits, and will be dependent on the schedule of assessments for each variable independently. The exception will be Week 76 visit window. The upper limit of the Week 76 visit window will be 3 days prior to the next obinutuzumab or placebo infusion or 30 days beyond Week 76 whichever is shorter.

As 24-hour UPCR has been collected less frequently than the spot UPCR, the 24-hour UPCR will be windowed based on spot UPCR's schedule of assessments.

If there are multiple values in the same window, values closest to the scheduled study day will be used in the analysis. If two or more values are equidistant from the scheduled study day, the latest assessment will be used. For each patient, the day of first blinded infusion of obinutuzumab or placebo will be designated study Day 1. Each assessment will be assigned a study day calculated as:

date of assessment -date of first dose +1

Baseline definition: Baseline is defined as the last non-missing value prior to the receipt of blinded infusion of obinutuzumab or placebo. Typically, baseline will be the pre-dose Day 1 assessment, but may include screening results if the pre-dose Day 1 result is not available or missing.

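### Read literally, the SAP's tie rule makes the post-infusion reading the vital-sign value at 5 of 7 post-baseline visits, so the by-visit change from baseline mixes infusion-day response with between-visit change

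*SAP*

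**What the plan says.** Change from baseline in targeted vital signs is a named safety endpoint (Protocol 2.2, SAP 1.1.2). SAP 4.5.4 is the SAP's only analysis text for it. That section lists baseline and seven post-baseline visits (Weeks 2, 4, 24, 26, 50, 52, 76), describes repeated readings at infusion visits, and ends: "Changes in vital signs from baseline will be summarized by visit".

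The collection schedule is in Protocol Appendix 1, Table 1, footnote d: "Vital signs should be taken pre-infusion, then in seated or semi-supine position, every 15 minutes for 1 hour, then every 30 minutes", continuing to the end of the infusion, with a further reading within 30 minutes after it. The investigator may add more.

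The General Consideration text of SAP Section 4 sets the rules for choosing a value:

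- Windows: they "will be dependent on the schedule of assessments for each variable independently".
- Several values in a window: "If there are multiple values in the same window, values closest to the scheduled study day will be used in the analysis".
- Ties: "If two or more values are equidistant from the scheduled study day, the latest assessment will be used".
- Study day: "date of assessment -date of first dose +1".
- Baseline: "Baseline is defined as the last non-missing value prior to the receipt of blinded infusion of obinutuzumab or placebo".

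The Week 76 window and 24-hour UPCR get special treatment there. Vital signs do not.

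**The concern.** A by-visit table of change from baseline is normally read as the course of blood pressure or pulse over the trial. That reading needs the same kind of measurement at each visit. Here baseline is taken before an infusion, while the rule appears to select a value taken after one at most later visits. At those visits the tabulated change contains both the between-visit change and the response to that day's infusion, and the table cannot separate them. Weeks 4 and 76 carry only the between-visit part. A step between Week 52 and Week 76, for example, could come from the switch in reading type alone.

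Two features of the design add to this. At Week 50 the two obinutuzumab arms receive different infusions but are summarised as one group. Patients who have stopped infusions still attend visits through Week 76 (Protocol 3.1.4) and have no post-infusion reading, so they contribute a different type of value to the same visit mean.

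**Working it through.** The plan states no figure for this point, so there is none to reproduce. The check applies the SAP rule to the scheduled readings.

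**1. Visits affected.** Post-baseline vital-sign visits (SAP 4.5.4): Weeks 2, 4, 24, 26, 50, 52, 76, which is 7. Blinded infusions (SAP 1.2.1): Day 1 and Weeks 2, 24, 26, 50, 52. The overlap after baseline is Weeks 2, 24, 26, 50, 52, which is 5. So 5 of 7 visits are infusion visits. Weeks 4 and 76 are not.

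**2. Readings per infusion visit.** Uninterrupted durations are 255 minutes for the first infusion and 195 minutes for later ones (Protocol Appendix 6).

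- 195 minutes: 1 before; 8 during (15, 30, 45, 60, 90, 120, 150, 180 minutes); 1 after. Total about 10.
- 255 minutes: 1 before; 10 during (the same 8 plus 210 and 240 minutes); 1 after. Total about 12.

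**3. Applying the rule.** Distance = |study day − scheduled day|, in whole days. All readings on one infusion date have the same study day, so they have the same distance. This holds for every visit offset from −3 to +3 days. The tie rule then takes the latest, which is the scheduled post-infusion reading or a later discretionary one. The result is the same at all 5 infusion visits. Over 5 such visits about 5 × 10 = 50 scheduled readings are taken, and 5 × 1 = 5 enter the by-visit change summary.

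**4. What each visit estimates.** Let b be the true between-visit change and d the mean difference between post-infusion and pre-infusion readings on one day.

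| Visit | Value selected | Mean change shown |
|---|---|---|
| Weeks 2, 24, 26, 50, 52 | post-infusion | b + d |
| Weeks 4, 76 | ordinary | b |

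If a fraction s of patients attending an infusion visit has stopped infusions, the shown change is b + (1 − s)d. The documents give neither d nor s. If d for systolic pressure were 5 to 10 mmHg (an assumption with no basis in the documents) and s = 0, 5 of the 7 visit means would shift by 5 to 10 mmHg.

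**5. Week 50.** Obinutuzumab patients are split 1:1 between the two arms (SAP 1.2.1), so 126 / 2 = 63 are planned in each. Arm 2 receives placebo at Week 50 (Protocol 3.3.1). The combined infusion-day response is then 0.5 × (response to obinutuzumab) + 0.5 × (response to placebo). Any acute effect specific to the drug would appear at half its size in the contrast with placebo at Week 50, but at full size at the other four infusion visits.

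**6. Day 1.** Readings after the first infusion starts are not baseline and belong to no listed post-baseline visit. By the count in step 2, about 12 − 1 = 11 readings per patient have no place in the by-visit change summary.

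**The case against.** **The mechanism is inferred.** The SAP never says that the latest assessment means clock time among planned timepoints on one date, and a by-visit summary does not rule out separate rows per timepoint. This stands as a limit: the result follows from a general rule and is not a stated choice for vital signs. It does not remove the need for the change. If the tie rule does not apply, the SAP has no rule for choosing among about 10 same-day readings.

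**The schedule calls for assessments before infusion unless otherwise specified.** Footnote d specifies otherwise for vital signs, and that note governs collection, not which value is analysed.

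**Both arms are infused.** Both receive blinded infusions and the same premedication, so a common shift affects both alike and the arms are compared at like timepoints. This largely stands. The difficulty is what within-arm change means, its comparability across visits, and the Week 50 blend.

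**The infusion-time data are used elsewhere.** A reader might infer that these readings go unused. The documents do not support that. Vital-sign abnormalities that cause symptoms, change treatment, prompt intervention or are judged clinically significant must be reported as adverse events (Protocol 5.3.5.6). Signs and symptoms of infusion reactions have their own form (Protocol 5.3.5.1). Systemic infusion reactions are events of special interest (Protocol 5.2.3) and are summarised under SAP 4.5.2. Protocol 6.4 plans vital-sign abnormalities displayed by time, and SAP Appendix 1 does not list that display as dropped. The narrower gap is that SAP 4.5.4 does not carry the display forward, whereas SAP 4.5.3.1 does so for laboratory abnormalities.

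**Posture and premedication.** A reader might also attribute the post-infusion difference to these. That contrast is not established. Protocol 4.5.4 allows semi-supine readings before infusions as well. Premedication is completed 30 to 60 minutes before the infusion (Protocol 4.3.2.2), and a pre-infusion reading is not required to precede it.

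**Conclusion.** The point holds for the by-visit summary of change from baseline in vital signs. On a literal reading, 5 of 7 post-baseline visits compare a post-infusion value with a pre-infusion baseline, two visits do not, and Week 50 blends active and placebo infusions within the combined group. This rests on three assumptions: the tie rule applies to vital signs, latest means latest in clock time, and the infusion date is the date nearest the scheduled day.

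The consequence is limited to a descriptive safety output. No efficacy test, estimand or multiplicity step depends on it. A reader might conclude that lasting change cannot be read from the table at all. That goes too far, because Weeks 4 and 76 still show change without an infusion, and Week 76 is the end of the primary period. The size of any shift in mmHg is unknown from the documents.

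**What to change.** In SAP 4.5.4, exempt vital signs from the tie rule and name the pre-infusion reading as the visit value at infusion visits. The number of post-baseline visits comparing a post-infusion value with a pre-infusion baseline then falls from 5 of 7 to 0 of 7. Patients who have stopped infusions also contribute a comparable reading.

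Optionally, carry the protocol 6.4 display of vital-sign abnormalities by time into SAP 4.5.4, so that infusion-day readings, Day 1 included, are summarised by arm. Day 1 is worth including because Protocol 5.1.1.1 reports for the Phase II obinutuzumab arm: "Of the 10 patients, the IRRs occurred at the first infusion in 8 patients".

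Both changes use data already collected. The cost is SAP wording and minor programming.

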4.6 OTHER ANALYSES

4.6.1 Summaries of Treatment Group Comparability/Demographics and Baseline Characteristics

Summaries by obinutuzumab (combined treatment groups) and placebo groups for clinically important demographic and baseline characteristics will be provided. The variables will be summarized using means, standard deviations, medians, and ranges for continuous variables and proportions for categorical variables. The baseline summary will include:

- Age (years)
- Sex
- Weight (kg)
- Race
- Ethnicity
- Region
- Serum Creatinine
- eGFR
- UPCR
 - 24-hour UPCR
 - Proportion of patients with UPCR ≥3
- anti-dsDNA (>120 IU/mL vs ≤120 IU/mL)
- C3 (<0.9 g/L vs. ≥0.9 g/L)
- C4 (<0.1 g/L vs. ≥0.1 g/L)
- Serum albumin
- LN classification
 - Proportion of patients with Class III
 - Proportion of patients with Class IV
 - Proportion of patients with concomitant Class V
- Duration of LN (months)
- Prior history of LN
- SLEDAI-2K

4.6.2 Pharmacokinetic Analyses

Serum obinutuzumab concentrations and observed PK estimates by non-compartmental analysis (NCA) will be summarized (mean, minimum, maximum, SD and geometric mean and geomean CV) and reported in this study. In addition, non-linear mixed effects modeling will be used to analyze the dose-concentration-time data of obinutuzumab. PK data will be used to refine a previously developed population PK (PopPK) model describing obinutuzumab PK following IV administration to LN patients including the effect of major covariates on the main PK parameters (e.g., clearance). Derivation of individual measures of exposure such as area under the serum-concentration time curve (AUC) and maximum observed concentration (C_{max}) will depend on the final model used for the analysis. The PopPK analysis will be preceded by exploratory graphical evaluations of the data and will be used to assess the relationships between obinutuzumab exposure and efficacy and obinutuzumab exposure and safety. Relevant observed relationships between exposure and safety parameters and exposure and efficacy may be further characterized using different approaches such as logistic regression analyses. Additional PK and PD analyses may be conducted as appropriate. Results of the population PK and exposure-response/PD analyses may be reported separately.

4.6.3 Immunogenicity Analyses

The immunogenicity analysis will be based on the safety population.

The numbers and proportions of ADA-positive patients and ADA-negative patients at baseline (baseline prevalence) and after drug administration (post baseline incidence) will be summarized by treatment group. When determining post baseline incidence, patients are considered to be ADA positive if they are ADA negative or have missing data at baseline but develop an ADA response following study drug exposure (treatment-induced ADA response), or if they are ADA positive at baseline and the titer of one or more post baseline samples is at least≥4-fold greater than the titer of the baseline sample (treatment-enhanced ADA response). Patients are considered to be ADA negative if they are ADA negative or have missing data at baseline and all post baseline samples are negative, or if they are ADA positive at baseline but do not have any post baseline samples with a titer that is≥4-fold greater than the titer of the baseline sample (treatment unaffected).

Additional analyses to assess the relationship between ADA status and safety, efficacy, PK and biomarker endpoints may be conducted as appropriate. Results of the analyses may be reported separately.

